## **3.0 Background\***

**3.1** Since 2010, The Center to Reduce Cancer Health Disparities (CRCHD) has managed the NON, (National Outreach Network) of CHEs (Community Health

**PROTOCOL TITLE: Education about Health and Cancer Study**

Educators) located within NCI-funded cancer research programs. The program seeks to enhance the integration of underserved communities into the research and mission of NCI and strengthen NCI's responsiveness to the cancer information needs of underserved communities. It is expected that the close affiliation of NON CHEs with other NCI-research programs will further strengthen the ability of NCI and DCC to reach underserved communities through region-based community education/outreach activities to disseminate cancer information aligned with NCI's research priorities. Through embedding this national network of CHEs in cancer centers throughout the nation, this has led to the development, implementation, and assessment of a broad range of culturally-tailored community outreach activities.

In 2019, DCC received a supplemental grant from NCI to continue to participate in the National Outreach Network and to continue to employ a Community Health Educator at the cancer center. Under the new award, NCI/CRCHD requires that every cancer center with the supplemental grant participate in a national effort to educate underserved communities (in our case, rural communities) about clinical trials/research, because underserved communities are often also underrepresented in trials/research.

**3.2** A 2007 systematic review looking at the barriers to recruiting underrepresented populations into cancer clinical trials found that lack of education about clinical trials was among the most commonly-reported barriers to participating in cancer clinical trials. The review did not identify any studies that reported on effectiveness of culturally-tailored education on clinical trials enrollment, and more research is needed in this area. A 2001 study also found that improving awareness/understanding of clinical trials may be an important step in improving attitudes toward clinical trials and, possibly, participation in trials.

**3.3.** In order to implement education about clinical trials across 24 cancer centers, NCI/CRCHD has developed a set of key messages that all cancer centers must include in their educational activities, and the cancer centers are tailoring the educational messaging/curriculum and delivery of activities to be locally-relevant and tailored to the needs of our catchment area. NCI/CRCHD has also developed a pre-test and a post-test (surveys- see attached) that will be administered immediately preceding and proceeding our educational activities, with the intent of evaluating whether the educational interventions changed the participants' knowledge of, attitudes toward, and behavioral intentions regarding taking part in clinical trials and research. NCI/CRCHD has asked us to track whether participants in our interventions go on to enroll in trials/studies in the six-months following our intervention (via our PIs' and Office of Clinical Trials' research records).

PROTOCOL TITLE: Education about Health and Cancer Study

This study will help measure and evaluate the effectiveness of different models of educating people about clinical trials. The data will be aggregated at a national level to assess the overall NCI/CRCHD activity. The data will be analyzed at the local/regional level to inform DCC's Community Outreach and Engagement program's future outreach models. Given the limited literature regarding the effectiveness of education on clinical trials knowledge, attitudes, and enrollment, this study will contribute meaningful and important information.

References:

- 1 *Ford, J. G., Howerton, M. W., Lai, G. Y., Gary, T. L., Bolen, S., Gibbons, M. C., ... & Powe, N. R. (2008). Barriers to recruiting underrepresented populations to cancer clinical trials: a systematic review. Cancer: Interdisciplinary International Journal of the American Cancer Society, 112(2), 228-242.*
2. *Taylor, H., & Leitman, R. Misconceptions and lack of awareness greatly reduce recruitment for cancer clinical trials.[article online, Health Care News, Vol. 1, Issue 3]. Rochester (NY): Harris Interactive, Inc.; 2001 Jan 22 [cited 2001 Mar 29]. [3 p].*

## **4.0 Study Endpoints\***

**4.1** Knowledge, attitudes, and behavioral intentions (assessed via surveys)

**4.2** Actual enrollment into a clinical trial or cancer research study (assessed via DCC Office of Clinical Research enrollment records over 6 months post intervention and enrollment records for specified DCC trials/research studies (see enclosed document with information about those studies)

## **5.0 Study Intervention**

**5.1** DCC's Community Outreach and Engagement Team ([name], , [name], [name], [name], [name], [name], [name], [name]) will implement the clinical trials education in experimental arms— 1) education using electronic provider alerts (BPA) and 2) an online website/video format. The education in both formats will be based on a set of key messages that cover information about clinical trials, including what they are, the benefits, the risks, and how to locate available clinical trials (see attached outline of education).

Experimental Arm 1 (Aim 1a):

We will evaluate educational outputs from electronic portal regarding what clinical trials and cancer research studies are. The educational content for videos was developed with the National Cancer Institute (NCI) toolkit as a foundation, with additional content added to adapt to our local institution, culture, and patient needs. The videos learning objectives focus on improving participants' knowledge about what clinical trials and cancer research studies are and how to access trials and studies, increase positive attitudes toward participating in trials and studies, and increase their intent to enroll in trials and studies.

**PROTOCOL TITLE: Education about Health and Cancer Study**

Providers will receive a BPA indicating patient may qualify to participate in the education survey. See enclosed invitation language. Providers will also have the option to include After Visit Summary (AVS) to Patient Notes that will contain invitation link. Patients will receive a link to the survey. If they choose to take part in the study, they will do so by completing the online consent, eligibility screening, pre-test, and contact information before the class they are registered for; attend the class; and complete the post-test after the class to assess achievement of the learning objectives. They will also be asked a series of questions to assess their eligibility for existing DCC clinical trials and research studies (see enclosed Qualtrics PDF).

**Experimental Arm 2 (Aim 1b):**

Participants will watch a video and view website materials ('online module') developed by DCC using messaging provided by the National Cancer Institute (NCI) and tailored to our local context. The online module's learning objectives will focus on improving participants' knowledge about what clinical trials and cancer research studies are and how to access trials and studies, increase positive attitudes toward participating in trials and studies, and increase their intent to enroll in trials and studies. Eligible participants will complete pre- and post-surveys to assess achievement of the learning objectives, and they will also be asked a series of questions to assess their eligibility for existing DCC clinical trials and research studies (see enclosed questions).

## **6.0 Procedures Involved\***

### **6.1 Experimental Arm 1 (Aim 1a):**

Out study will be largely advertised to DCC's patients and caregivers (e.g., through Patient and Family Support Services' catalog, DH events calendar, DCC/ DH Facebook, online listserves, waiting rooms)..

- a- Recruitment- recruitment to participate in the study will happen after a patient or caregiver receives a link to participate in survey from provider BPA. DCC providers open a message from electronic provider portal BPA. The BPA prompts an alert to providers – who open a message indicating the option to send a patient information about accessing the survey or, to be connected with a clinical nurse/coordinator who can walk the patient through the process of accessing the survey.  
1 – Provider portal option using electronic medical record portal EDH/Epic includes option inviting providers to click on Best Practice Alert when prompted.
- b- The recruitment language provides prospective participants with a link to an online survey where they can consent, complete eligibility screening, the pre-test, and contact information. Contact information (name, email, phone number, address) and date of birth is collected to facilitate: 1) hand-off to open studies/trials' teams and clinical staff (Research Nurses/Nurse Navigators) for recruitment, 2) tracking subsequent enrollment into any study/trial, 3) gift card distribution for their time, and 4) to invite them to

PROTOCOL TITLE: Education about Health and Cancer Study  
complete the post-test.

- d- Provision of participant compensation for completing pre-test. E-gift cards that have not been claimed six months after being emailed may be deactivated.
- e- Assignment of unique numeric identifiers to link records
- f- Completion of an online post-test survey (see attached Qualtrics PDF for Experimental Arm 1)- including:
  - Post-intervention knowledge
  - Pre-screening for eligibility into pre-selected open trials/studies at DCC(see attachment with study details and questions).
  - Post-intervention attitude and behavioral intention questions
- g- Provision of participant compensation for completing the post-test. E-gift cards that have not been claimed six months after being emailed may be deactivated.
- h- Referral to pre-screened (possibly eligible) participants to PI's of pre-selected open studies/trials, as well as DCC clinical staff (research nurses, nurse navigators). This will entail providing participant contact/health information to PIs/study teams/DCC clinical staff of studies/trials that the participant may be eligible for. Participants will have provided permission for their information to be shared (see information sheet and pre-screening section of the Qualtrics post-survey). Tracking of participants' enrollment status into studies/trials over six months (via PI/study team records and DCC Office of Clinical Research records/Oncore).  
This will entail providing our participants' identifying information to the PIs/research teams of selected studies and to DCC's Office of Clinical Research and asking them to identify which participants have enrolled in studies/trials since the educational intervention. With permission/direction from DCC's Office of Clinical Research, our study team members may track enrollment via Oncore. See enclosed Excel spreadsheet that will be used for tracking. [We will also collect aggregate enrollment in trials/studies at DCC for comparison with our participants.]

**PROTOCOL TITLE:** Education about Health and Cancer Study

- i- Transmission of de-identified pre and post survey data files to NCI/CRCHD and/or its contractor for data entry, quality control, and national aggregation; e-mailing of tracking excel spreadsheet to NCI/CRCHD and/or its contractor.
- j- Local analysis of data to determine effect of study objectives

**Experimental Arm 2 (Aim 1b):**

The video and online education module arm will feature the following key elements:

- a- Geo-targeted paid advertisements and other unpaid posts on social media (e.g., Facebook), listserves, or flyers will invite prospective participants to our study by asking them to click 'Learn More' to open the surveys in a new page in Qualtrics (see enclosed recruitment messaging). We will also recruit through other online opportunities, such as Front Porch Forum, e-newsletters and listservs, online community forums/groups, partner organizations, etc.
- b- A consenting process utilizing a downloadable information sheet (see attachments- information sheet with e-signature)
- c- Screening for eligibility questions- Prospective participants will be asked a series of questions to ascertain if they are adults living in rural VT or NH (see Qualtrics survey PDF). Those who are eligible and consented will be told they are eligible and invited to continue forward into the study. Those who are not eligible will be thanked for their time. All questions will be programmed as required.
- d- Completion of a pre-test survey (see Qualtrics survey PDF)- includes demographics; baseline knowledge, attitudes, and behavioral intentions. (see Qualtrics survey PDF). All questions will be programmed as required.
- e- Delivery of online module as the educational intervention (as described earlier- see enclosed link to module: <https://cancer.dartmouth.edu/node/1167>). The online module will include a video and accompanying educational information (not yet visible to the general public but may be used in select venues outside of research project).
- p- Completion of a post-test survey (see Qualtrics survey PDF)- includes knowledge and attitudes questions. All questions will be programmed as required.

**PROTOCOL TITLE: Education about Health and Cancer Study**

- q- Pre-screening for eligibility into pre-selected open studies and other clinical trials at DCC (see Qualtrics survey PDF). All questions will be programmed as required.
- r- Completion of a post-test survey (see attachment and Qualtrics survey PDF)- behavioral intention questions. All questions will be programmed as required.
- s- Collection of contact information (name, email, phone number, address) and date of birth to facilitate: 1) hand-off to open studies/trials' teams and clinical staff (Research Nurses/Nurse Navigators) for recruitment, 2) tracking subsequent enrollment into any study/trial, and 3) gift card distribution for their time. All components of the contact information/identifying information fields will be programmed as required (see PDF of Qualtrics survey).
- t- Provision of participant compensation for their time via emailed e-gift cards. E-gift cards that have not been claimed six months after being emailed may be deactivated.
- u- Assignment of unique numeric identifiers to de-identify all survey data for sharing with NCI/CRCHD
- v- Connection of pre-screened (possibly eligible) participants to PI's of pre-selected open studies/trials. This will entail providing participant contact/identifying information to PIs/study teams of studies/trials that the participant may be eligible for, as well as connection of pre-screened (possibly eligible participants) to the cancer center's clinical team (Research Nurses/Nurse Navigators) to explore available clinical trials/establish care. Participants will have provided permission for their information to be shared (see information sheet and Qualtrics survey PDF).
- w- Tracking of participants' enrollment status into the pre-selected open studies/trials and other DCC clinical trials over six months (via PI and DCC Office of Clinical Research records/Oncore). This will entail providing our participants' identifying information to the PIs of selected studies and to DCC's Office of Clinical Research and asking them to identify which participants have enrolled in studies/trials since the educational intervention. With permission/direction from DCC's Office of Clinical Research, our study team members may track enrollment via Oncore. See enclosed Excel spreadsheet that will be used for tracking.
- x- E-mailing de-identified pre and post survey data to NCI/CRCHD and/or its contractor for data entry, quality control, and national aggregation. E-mailing of tracking excel spreadsheet to NCI/CRCHD and/or its contractor.
- y- Local analysis of data to determine effect of study objectives

If any individuals contact the research team indicating they had difficulties completing the surveys online, we will seek information from them to match their survey record (e.g., their initials, time of day/date they were completing the survey) and provide them with assistance by phone and/or email to enable them to complete the study procedures. In some cases, this may entail providing a separate survey link to them by

PROTOCOL TITLE: Education about Health and Cancer Study  
email for them to complete.

PROTOCOL TITLE: Education about Health and Cancer Study

We are discontinuing our control arm. Because the control arm was part of our local research procedures and not part of NCI's national initiative, we will not be providing any control arm data to NCI or its contractor.

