## **2.0 Objectives\***

**2.1** The purpose of this project is to: (1) contribute to a nation-wide initiative to educate the public about clinical trials, (2) evaluate the effectiveness of education about clinical trials/research in changing knowledge, behavioral intentions, and behaviors related to clinical trials/cancer research enrollment.

Aim 1: Implement and evaluate educational activities to improve knowledge of, attitudes and behavioral intentions toward, and participation in clinical trials and cancer research studies among rural residents living in NH and VT (Rural = RUCC 7-9 counties).

Aim 1a: Implement electronic portal education regarding what clinical trials and cancer research are and evaluate the effect on knowledge of, attitudes and behavioral intentions toward, and actual enrollment into clinical trials and cancer research studies.

Aim 1b: Implement online education regarding what clinical trials and cancer research are and evaluate the effect on knowledge of, attitudes and behavioral intentions toward, and actual enrollment into clinical trials and cancer research studies.

Aim 1c: Compare the impact of electronic education about clinical trials with the impact of an innovative outreach modality using social media, patient portals and web-based technology for educating the public about clinical trials.

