## **2.2 Hypotheses:**

- 1- Assessing education about clinical trials will be effective in: a) increasing knowledge of clinical trials; b) increasing intent to participate in clinical trials; and c) increasing clinical trials/research project enrollment within six-months post-outreach.
  
- 2- Online/video outreach with online module about clinical trials will be effective in: a) increasing knowledge of clinical trials; b) increasing intent to participate in clinical trials; and c) increasing clinical trials/research project enrollment within six-months post-outreach.

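### In Arm 2, post-test intention is asked only after mandatory pre-screening for open trials, so its pre/post change is not that of the online education alone

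*Protocol*

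**What the plan says.** Section 6.0, Experimental Arm 2, lists the survey steps in this order:

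- Step d, the pre-test: "includes demographics; baseline knowledge, attitudes, and behavioral intentions".
- Step e, the online module, which that step itself names as the educational intervention.
- Step p: "Completion of a post-test survey (see Qualtrics survey PDF)- includes knowledge and attitudes questions".
- Step q, pre-screening for pre-selected "open studies and other clinical trials at DCC (see Qualtrics survey PDF). All questions will be programmed as required".
- Step r: "Completion of a post-test survey (see attachment and Qualtrics survey PDF)- behavioral intention questions".

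The purpose of the measurement is stated in four places:

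- Aim 1b (Section 2.1): "Implement online education regarding what clinical trials and cancer research are and evaluate the effect on knowledge of, attitudes and behavioral intentions toward".
- Hypothesis 2 (Section 2.2): "Online/video outreach with online module about clinical trials will be effective in: a) increasing knowledge of clinical trials; b) increasing intent to participate".
- Section 3.3, on the national pre- and post-tests: they are "administered immediately preceding and proceeding our educational activities, with the intent of evaluating whether the educational interventions changed" knowledge, attitudes and intentions.
- Section 5.1, Arm 2: greater intent to enroll is one of the module's learning objectives, and "Eligible participants will complete pre- and post-surveys to assess achievement of the learning objectives". The eligibility questions are then mentioned as something asked in addition.

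The end of Section 6.0 says that the control arm is being discontinued. Step x sends the de-identified pre and post survey data for national aggregation.

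**The concern.** The question in hypothesis 2b is whether the online education raises intent to take part in trials. Between the education and the intention items, each participant is asked about eligibility for actual open studies and trials. That is not obviously neutral for this particular outcome: finding that one may qualify could raise stated intent, and finding that one does not could lower it. Section 19 adds that people who pre-screen as possibly eligible are asked to let their details be shared with study or clinical teams, although the place of that question in the Arm 2 survey is not shown.

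A change in intention reported under hypothesis 2b, or passed on for national aggregation, would be read as the effect of the education. It would also contain whatever the pre-screening did. A larger sample does not help, because the mixing comes from the order of the items and not from sampling error.

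There is a lesser consequence. A participant who closes the survey during step q gives no post-test intention answer, and Section 14.1 withdraws anyone without a completed post-test. The intention result is thus confined to people who went through pre-screening. The documents do not say how many leave at that step.

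**Working it through.** No figure in the protocol bears on this point, so the check sets the sequence against the stated purpose.

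**1. What each change spans.** Write E for the effect of the module, S for the effect of pre-screening, and O for everything else in an uncontrolled pre/post comparison (repeat testing, demand effects). On the Section 6.0 order:

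- Knowledge and attitudes, step d to step p, pass only step e: change = E + O.
- Intention, step d to step r, passes steps e and q: change = E + S + O.

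Each outcome has its own E, S and O; only the intention change contains an S.

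**2. Can S be separated from E?** This would need an intention measure between steps e and q, or a group that received the module without pre-screening, or a group that was pre-screened without the module. Section 6.0 provides no intermediate measure. The step q questions are required, so no completer skips that step. The control arm is gone. One observed change and two unknown effects leave S unidentified, and no analysis plan can recover it afterwards.

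**3. Does another section put intention elsewhere?** Section 22.0 gives a different Arm 2 sequence, with pre-screening ahead of the whole post-test. Intention still follows pre-screening there, so both descriptions agree on this point. They disagree on knowledge and attitudes, which is a separate item.

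**4. Is the purpose the education or the package?** Step e names the module as the intervention. Aim 1b, hypothesis 2b, Section 3.3 and the Section 5.1 learning objectives all attach the intention result to the education. No section says that the result includes pre-screening.

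**5. Arm 1.** Step f in Section 6.1 lists knowledge, then pre-screening, then attitudes and intention. If that list is an order, both attitudes and intention follow pre-screening. Section 5.1 mentions the Arm 1 eligibility questions after the post-test, but only as an additional set of questions. Section 5.1 uses near-identical wording for Arm 2, where Section 6.0 places those questions before the intention items, so the wording does not fix an order in either arm. The Arm 1 survey has to settle it.

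**The case against.** The strongest reply is that the sponsor is evaluating a package. Hypothesis 2 speaks of outreach with a module. Its part c, enrollment, depends on pre-screening and referral and shares a stem with part b. Section 17.1 speaks of changes resulting from any of the study arms. Section 5.1 describes the eligibility questions under the intervention heading, and for Arm 1 the protocol treats pre-screening as a section of the post-survey. This reading is arguable. It does not remove the mixing, and if it is what is meant, the protocol needs to say so, because its aim, hypothesis and survey purpose point to the education.

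The order also looks deliberate. The revision history records that revision 4 put the post-test ahead of the pre-screening questions, and that revision 5 re-ordered some post-test questions relative to the trial linkages. A reader might infer an oversight; the log suggests a choice. It gives no reason for the choice, and a deliberate order mixes the effects just as an accidental one does.

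A reader might also infer that the intention result is inflated. The documents do not support that: nothing shows that pre-screening moves intention at all, the survey content is not visible, and the effect could go either way. The number of participants exposed would describe reach, not bias.

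Finally, an uncontrolled pre/post change is weak evidence whatever the order. That stands. This contaminant is nevertheless avoidable, and step p already avoids it for knowledge and attitudes.

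**Conclusion.** The point holds in a limited form. The Arm 2 intention change measures education plus pre-screening, while the aim and hypothesis 2b describe education. The two parts cannot be separated from the data the design collects. The size and direction of the pre-screening part are unknown, so the finding is that the contrast does not match its stated question, not that it is biased by some amount.

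One of the three parts of hypothesis 2 is affected. On the Section 6.0 order, Arm 2 knowledge (2a) and attitudes are not; that would change if the survey follows Section 22.0. Enrollment (2c) is taken from records and does not depend on the order of survey items.

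The conclusion assumes that the fielded survey follows steps d to r as written. For Arm 1 the same problem is possible, and there for attitudes as well, but it is not established. The point should be corrected; it does not invalidate the study.

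**What to change.** - **Remaining Arm 2 participants.** Move the intention items to step p, directly after the module and before step q, and record a survey-version flag. The cost is one block moved, no items added, and an IRB modification. The downside is two survey versions, whose intention results should not be pooled without regard to the flag.
- **Data already collected, or if few participants remain.** Keep the order and report the intention change as the combined effect of education plus pre-screening, in local reports and in the data sent for national aggregation. This costs only wording. Current accrual is not stated, so the choice between the two routes rests with the sponsor.
- **If the package is the intended target.** Say so in hypothesis 2b and Section 5.
- **Arm 1.** Check the survey. If attitudes and intention do follow pre-screening, apply the same move or the same label.
- **Separately,** reconcile Section 22.0 with steps p to r so that one Arm 2 order is stated.

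Re-ordering removes one avoidable contaminant. The result remains an uncontrolled pre/post change and should not be described as a pure education effect.

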## **21.0 Economic Burden to Subjects**

**21.1** Study participants will not be subject to any costs for participating in the study/educational interventions.

Should our intervention be effective in encouraging them to participate in a clinical trial or research study, all costs associated with those trials/studies are beyond the scope of this study.

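### The six-month enrollment endpoint follows education plus pre-screening and active referral, but the aims and hypotheses credit education alone

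*Protocol*

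**What the plan says.** **Intervention.** Protocol 5.1 says the outreach team "will implement the clinical trials education in experimental arms", in two formats. The arm descriptions in section 5 add that participants answer questions on their eligibility for existing cancer-center studies. They do not mention that participants are then handed to recruiters.

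**Aims and hypotheses.** Section 2.1 reads "Aim 1b: Implement online education regarding what clinical trials and cancer research are and evaluate the effect on knowledge of, attitudes and behavioral intentions toward"; the sentence goes on to actual enrollment. Aim 1a is built the same way. In section 2.2, parts 1c and 2c predict that the education or online outreach will be effective in "increasing clinical trials/research project enrollment within six-months post-outreach".

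**Hand-off.** For Arm 1, section 6.1 step h sends those who may qualify both to the investigators of the chosen studies and to the center's research nurses or navigators. For Arm 2, section 6.0 step v provides for "Connection of pre-screened (possibly eligible) participants to PI's of pre-selected open studies/trials" and, as a second route, a connection to research nurses or navigators who help the participant look into available trials. Arm 1 step b and Arm 2 step s both give recruitment as the first purpose of collecting contact details. Sharing needs the participant's permission, and section 16.0 adds that the participant must be interested in being contacted.

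**Endpoint.** Section 4.2 takes enrollment from the Office of Clinical Research records over six months and from "enrollment records for specified DCC trials/research studies". Arm 2 step w tracks "enrollment status into the pre-selected open studies/trials and other DCC clinical trials over six months".

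**Analysis.** Section 17.1 reads changes in behavior as a result of the study arms. Nothing in the document distinguishes enrollments that followed a hand-off from those that did not.

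**The concern.** The hand-off acts directly on the outcome being counted. A participant who learned nothing from the module, was telephoned by a study team and agreed to join counts exactly like one who sought out a trial because of the module. Even a purely descriptive enrollment rate would be labelled as following education when it follows education and outbound recruitment together.

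This matters for what is done with the result. Section 3.3 says the local analysis will inform the center's future outreach models, and section 25.0 speaks of sustaining successful interventions. A center that kept the video and dropped the referral step on the strength of this endpoint might drop the component that produced the enrollments.

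The knowledge and attitude outcomes are not affected by the hand-off, which comes after the surveys. The point concerns enrollment only.

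**Working it through.** **1. The protocol's own arithmetic.** The only sample-size figures are in section 12.0: up to 900 consented, about one third completing, targets of up to 50 (Arm 1) and 200-250 (Arm 2). Check: 900 × 1/3 = 300 = 50 + 250. This reproduces and is not in dispute. The document gives no enrollment rate, referral rate or effect size, so no power calculation applies. The point rests on setting the sections side by side.

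**2. Tracing the chain.**

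| Element | Arm 1 | Arm 2 |
|---|---|---|
| Education | 5.1 | 5.1; 6.0 step e |
| Pre-screening questions | 5.1; 6.1 step f | 5.1; 6.0 step q |
| Hand-off to study teams | 6.1 step h | 6.0 step v |
| Hand-off to nurses or navigators | 6.1 step h | 6.0 step v |
| Recruitment stated as purpose | 6.1 step b | 6.0 step s |
| Six-month enrollment counted | 4.2; 6.1 step h | 4.2; 6.0 step w |
| Cause named in aims and hypotheses | education (1a, 1c) | education or online outreach (1b, 2c) |

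Three things follow.

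- No arm has education without the referral procedure, or referral without education. The data cannot separate the two.
- The problem is not confined to the pre-selected studies. The nurse or navigator route can lead to other cancer-center trials, which the endpoint also counts.
- The one comparator named for enrollment, aggregate cancer-center enrollment (6.1 step h, Arm 1 only), is not described as having gone through this study's pre-screening and hand-off. That it did not is an inference, though a natural one.

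**3. How large could it be?** All rates here are assumptions. Let *b* be background enrollment, *s* the share pre-screened and handed off, and *r* the share of those who enroll because of the hand-off. Set the education effect to zero. Then

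expected enrollments = n × (b + s × r).

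Take n = 250 (the Arm 2 upper target), b = 0 to 1%, s = 10 to 50%, r = 5 to 20%.

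- Lowest: 250 × (0 + 0.10 × 0.05) = 250 × 0.005 = 1.25 (0.5%).
- Highest: 250 × (0.01 + 0.50 × 0.20) = 250 × 0.11 = 27.5 (11%).
- Background alone: 250 × 0 = 0 to 250 × 0.01 = 2.5.

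A middle case with n = 225 and s = 20%: 225 × 0.20 = 45 handed off. With r = 5 to 15%, 45 × 0.05 = 2.25 and 45 × 0.15 = 6.75, or 1.0% to 3.0% of the arm.

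The calculation shows only that enrollments above background can appear with no education effect. It does not estimate what will happen. It covers Arm 2; Arm 1 draws on cancer-center patients and caregivers, whose background enrollment could differ.

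**The case against.** **The package is disclosed.** Section 5 includes the pre-screening questions, Hypothesis 2 speaks of outreach, both hypotheses count enrollment after outreach, and 17.1 attributes change to the arms as delivered. On this reading the fault is loose labelling. This stands in part: the pre-screening is in plain view. But the hand-off is absent from section 5, and the aims name education as the cause of enrollment.

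**It is only the missing control again.** The control arm has been discontinued, so enrollment could not be attributed to education even without referral. True, but restoring a no-contact control would still compare education plus referral with nothing. In the between-arm comparison of Aim 1c, referral is present on both sides and is not by itself a difference between the arms.

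**A breakdown by referral status belongs in an analysis plan.** Agreed. The missing cross-tabulation is not in itself a fault in the protocol. What the protocol does fix is the intervention, hypotheses and endpoint, and these do not match.

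**Referral is partly a consequence of education.** This is the strongest objection, and it stands. Permission and interest in being contacted are given after the education and may be raised by it. A reader might infer that enrollment among non-referred participants isolates the education effect. It does not. That group is selected on something that happened after the intervention, and using it would discard anyone whom the education moved to accept referral, probably understating the education effect.

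**Conclusion.** The point holds as one about attribution. As written, the plan would credit education with enrollments that follow education, pre-screening and active referral. The endpoint remains usable as a description of that package.

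Two stronger readings go beyond the documents. One is that most or all enrollments will come from referral: that follows only if unreferred enrollment is assumed to be near zero, and the protocol gives no rates. The other is that the education has no effect on enrollment: nothing shows this, and education may work partly by making people willing to be referred.

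The size is therefore unknown. The range of about 1 to 28 enrollments in 250, against 0 to 2.5 from background, rests wholly on the assumed rates. The conclusion itself needs none of them. It rests on the hand-off occurring in both arms, its stated recruitment purpose, and an endpoint that counts the same studies.

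**What to change.** 1. In 2.1, 2.2, 4.2 and 17.1, state that for the enrollment endpoint the intervention is education plus pre-screening and referral, and that no conclusion about education alone will be drawn from it.

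2. Report enrollment per arm, descriptively, by referral status, each group with its own denominator:
   - (i) participants handed to a specific study team, including those also connected to a nurse or navigator;
   - (ii) participants connected only to a research nurse or navigator;
   - (iii) participants with no hand-off.

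   The second group is needed because someone who reaches an unlisted trial through a navigator was neither referred to that trial nor left unreferred.

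3. State that group (iii) is not an estimate of the education effect, because accepting referral comes after the education and may be raised by it.

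**Cost.** Wording in four sections and one cross-tabulation of the referral and enrollment trackers. The protocol mentions both, but their fields are not shown, so it should be confirmed that they record which route each participant took. The price is a narrower conclusion for Hypotheses 1c and 2c.
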